#### *6.6.C. DESCRIPTION*

CalmTex® is an innovative polyester and elastane sensory fabric used in the production of JettProof sensory singlets. This unique construction is breathable and moisture wicking, with a 360-degree knitted stretch that moves with the body. Fitted according to chest measurement, JettProof sensory singlets are non-restrictive, and are intended to be fitted closely to the body and worn as a base garment or under other clothing. A full dosage wearing regimen was defined for this trial, through consultation with the manufacturer and stakeholders, as a minimum of 6 hours/day of continuous wear but can be extended up to 24 hours/day.

#### *6.6.D. CRITERIA FOR DISCONTINUATION/MODIFICATION*

Withdrawal of informed consent is possible at any time, without any obligation for the child or caregiver to give reasons for the decision. Tolerance, compliance, and adverse events will be monitored during each weekly assessment visit or by telephone call from a member of the research team. Should any serious adverse events or other concerns about wellbeing occur, the child will discontinue the intervention and return to standard care. In these such cases, the child will be invited to remain in the study and attend the remaining assessment visits.

#### *6.6.E. STRATEGIES TO IMPROVE/MONITOR ADHERENCE*

After the researcher has supplied child participants their singlet and supported their first wear, they will provide the caregiver with strategies to support and encourage their child's singlet wearing and manage challenging behaviour should it arise. A researcher will telephone the caregiver at least three times during the intervention phase – once each during each of the acclimatization and full-scale wearing weeks – to check how the child is doing and troubleshoot any issues arising. During the intervention phase, the length of time the child spends wearing the singlet will be reported each day by the caregiver via a smartphone-based experience sampling app.

#### *6.6.F. CONCOMITANT CARE AND INTERVENTIONS*

No concomitant care or intervention is prohibited during the trial. Caregivers will be asked to disclose any medications their child is taking (including type and dosage) and any outside care accessed during the trial period (including type and duration). Caregivers will be provided a one-page document summary of the study and nature of the child's involvement to share this with any clinicians involved in their child's care, if they wish to do so.

## 6.7. OUTCOMES

### 6.7.A. PRIMARY OUTCOMES

The primary outcomes for this trial are:

- Child sympathetic nervous system activity (i.e., heart rate, heart rate variability, electrodermal activity, and motion-based activity) acquired from an Empatica E4 wristband, worn in the context of Laboratory Temperament Assessment Battery (Lab-TAB; H. Goldsmith et al., 2010) episodes conducted in weeks 1 through 5. Empatica E4 recordings have been shown to accurately predict affective behaviour in autistic children (Goodwin, Mazefsky, Ioannidis, Erdogmus, & Siegel, 2019) and has been validated against other stationary and wearable biosensors (Schuurmans et al., 2020; van Lier et al., 2020).
- Child motor coordination as measured by the standardized Movement Assessment Battery for Children-2nd Edition (M-ABC-2; Henderson, Sugden, & Barnett, 2007) and Clinical Observations of Motor and Postural Skills (COMPS-2; B Wilson, Kaplan, Pollock, & Law, 2000) in weeks 1 and 5. The M-ABC-2 is one of the most widely used motor assessments in research and clinical practice (Barnett, 2008) with evidence of inter-rater reliability, test-retest reliability, content- and concurrent validity (Henderson et al., 2007). The COMPS-2 was designed to supplement standardized measures of motor performance and has demonstrated good inter-rater reliability, test-retest reliability, and construct validity (Brenda Wilson, Pollock, Kaplan, Law, & Faris, 1992).
- Child attainment of individualized and meaningful intervention goals as measured by Goal Attainment Scaling (GAS; Kiresuk & Lund, 1994). Upon study entry, the caregiver of each child will be supported by investigators to formulate two GAS goals centred around self-regulation difficulties for their child and develop a five-point descriptive rating scale for completion in weeks 1 and 5. Use of GAS is common in research and clinical practice and is especially sensitive to capturing change in intervention studies (McLaren & Rodger, 2003).

### 6.7.B. SECONDARY OUTCOMES

The secondary outcomes for this trial are:

- Child anxiety as measured by the caregiver-reported Spence Children's Anxiety Scale-Parent Version (SCAS-P; Nauta et al., 2004) in weeks 1 and 5. The SCAS-P has strong properties (Nauta et al., 2004; Orgiles, Fernandez-Martinez, Guillen-Riquelme, Espada, & Essau, 2016) including good internal consistency and convergent, divergent and discriminant validity among autistic children (Magiati et al., 2017).
- Child affect and sleep reported daily by caregivers via smartphone-based experience sampling. The experience sampling method demonstrates high ecological validity, in that it captures real-life experiences and behaviours across a full range of momentary contexts while 'in-the-moment', thus circumventing potential biases from retrospective recall.
- Child reactivity and self-regulation as coded from behaviour during semi-structured Lab-TAB (H. Goldsmith et al., 2010) episodes in weeks 1 through 5. Being a direct observational method, the Lab-Tab will provide a method by which to build upon and complement caregiver

ratings of child affect. Lab-TAB episodes have been validated as effective for inducing emotional reactivity in autistic children (Macari, Verneti, & Chawarska, 2021; Northrup et al., 2020) and used previously as a context for physiological recording (Nuske et al., 2022).

[figure not shown]
### 6.7.C. OTHER OUTCOMES

Other outcomes of this trial include:

- Intervention feasibility and acceptability indicated through duration of daily singlet wear – as captured through experience sampling – and semi-structured interviews conducted with children and their caregiver(s) in weeks 0 and 5. This will provide valuable first-hand insights into the feasibility and acceptability of JettProof sensory singlets.
- Caregiver effort expended to support their child as measured by the Parent Effort Scale (PES; Pfeiffer et al., 2017) in weeks 1 and 5. The PES has shown adequate internal consistency and test-retest reliability in an autistic sample (Bevans, Hallock, Piller, & Pfeiffer, 2022).
- Caregiver stress as measured by the Parent Stress Index-4th Edition Short Form (PSI-4-SF; Abiden, 2012) in weeks 1 and 5. The PSI-4-SF has shown good internal consistency and test-retest reliability in a variety of samples (Abiden, 2012).

## 6.8. PARTICIPANT TIMELINE

Figure 1 shows the schedule of participation in the study.

**Figure 1.** Schedule of Participation.

### 6.8.A. INTAKE AND CHARACTERIZATION

Caregivers who express interest in having their child participate in the study will be telephoned by a member of the research team to conduct eligibility screening including verbal administration of the

SRS-2 (Constantino & Gruber, 2012), SSP (McIntosh et al., 1999) and PPECS (Dewart & Summers, 1995). This phone call will require a time commitment of approximately one hour for caregivers.

For those who meet trial eligibility criteria, an appointment will be made to attend LTU for a face-to-face assessment. Once an appointment has been made, caregivers will be emailed an appointment confirmation letter along with a Participant Information and Consent Form (PICF) that contains: a description of the purpose of the study, the study procedures and timeframe, the possible risks and potential benefits to participation, compensation for being involved, procedures to protect confidentiality and privacy, and the contact details of the research team and HREC.

On entry to the study (week 0), child participants will attend a face-to-face entry visit with their caregiver(s) which will involve a researcher taking caregiver consent and additional child verbal assent, taking the child's chest measurement (for supply of appropriate singlet size), conducting a brief interview with the child and caregiver to determine their motivations for participating. At this visit, children will be given a printed visual schedule of the study procedures and timeline in the form of a booklet to take home with them. Further, the researcher will work with the caregiver to identify one or two goals for their child during the intervention, support them to install a smartphone application (MyCap) for experience sampling and demonstrate its use, provide them with a hardcopy Demographic and Medical History Questionnaire, and navigate them to Pearson's Q-global web-based platform for completion of the Vineland Adaptive Behaviour Scales-3rd Edition (Vineland-3; Sparrow, Cicchetti, & Saulnier, 2016). Caregivers will complete these questionnaires on-site during their child's assessment visit or finish them at home before their child's next assessment visit. This assessment visit will require a time commitment of approximately two hours for the child and their caregiver(s).

#### *6.8.B. INTERVENTION SCHEDULE*

The end of the week 0 visit will mark the beginning of the trial period, and first intervention phase. Children will continue with their standard care for the first trial week (i.e., week 1; pre-intervention/baseline phase A), with no restrictions on concomitant care or intervention (including medications). Week 2 will be a period of acclimatization (pre-intervention/acclimatization phase B), allowing children to practice wearing the singlet and increase the duration of daily use in their own time. The researcher will telephone the caregiver during this week to check how they are doing and to troubleshoot any issues, completing a further follow-up call if needed. Weeks 3 and 4 will be the full intervention phase (intervention phase B), whereby children are encouraged to wear their singlet for as long as they feel comfortable. There will be no restrictions regarding wearing times or contexts, nor regarding access to outside care or interventions, during the intervention phases. Children will cease wearing their singlet and return to their standard care in week 5.

#### *6.8.C. ASSESSMENT SCHEDULE*

Child participants will attend six face-to-face assessment visits (See Figure 1 & Table 1) with their caregiver(s) during each of the trial weeks. Assessment visits at weeks 1 through 5 will each involve a researcher fitting the child with an Empatica E4 wristband on the wrist or calf. Empatica E4 recordings will be taken while children watch a low-demand movie (Inscapes) to ascertain their physiological baseline, and while completing Lab-TAB (H. Goldsmith et al., 2010) episodes interspersed with a period

of free-play with their caregiver. Additional assessments conducted at weeks 1 and 5 include the M-ABC-2 and COMPS-2, and at week 5 an examiner-led interview to explore child and caregiver perceptions and experiences of the singlet. All assessment sessions will be video-recorded with consent from caregivers for later scoring.

The caregiver will be given a laptop during each of their child's assessment visits and navigated to a REDCap survey to complete: GAS (Kiresuk & Lund, 1994) in weeks 1 through 5, in addition to the SCAS-P (Nauta et al., 2004), PES (Pfeiffer et al., 2017). Additionally, the PSI-4-SF (Abiden, 2012) will be completed via hardcopy in weeks 1 and 5. Caregivers who do not manage to complete all survey measures during their child's assessment visit will be provided a survey return code, enabling them to return to the survey for later completion (within 24 hours). The PSI-4-SF may be taken home for completion and return at the child's next assessment visit. Assessment visits in Weeks 2, 3 and 4 will require a time commitment of around one hour for children and their caregiver(s). A longer time commitment of two hours will be required for visits in Weeks 1 and 5.

During the trial period, the caregiver will receive a push notification on their smartphone from their installed MyCap application three times per day (morning, afternoon, evening) to report their child's previous night's sleep (morning, only), current activity, affect, use of non-routine medications (evening, only), and singlet wearing (intervention phases, only). The resulting daily time commitment for caregivers will be approximately 6 minutes (2 minutes per day).

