A total of 802 testimonials – posted by customers to the JettProof website between June 2015-October 2021 – were analyzed for prominent themes using NVivo software ([name], unpublished data). The results of our analysis revealed three key themes. The first theme, *acceptability*, revealed that most users found the garments comfortable and enjoyed wearing them alone or under other clothing; however, some testimonials mentioned needing an ‘adjustment period’ to acclimate to the garments. The second theme, *effects*, demonstrated multifaceted effects of JettProof sensory garments on: arousal, sensory processing, sleep, engagement/attention, and participation. Effects of JettProof garments were reported across settings (i.e., school, home, community, and clinical) and also for the broader family unit. Further, testimonials suggested a short duration of effect (i.e., only while wearing) and both immediate and delayed latencies. The third theme, *usage*, revealed that most users of JettProof garments were diagnosed with Autism Spectrum Disorder (ASD), or had other developmental or clinical presentations including: anxiety, Attention-Deficit Hyperactivity Disorder (ADHD), sensory sensitivities, and motor conditions (e.g., Dyspraxia). Further, testimonials indicated that most users wore JettProof sensory garments throughout the entire day and overnight, with others wearing the garments in challenging contexts (e.g., while at school).

Conclusions from our testimonial analyses were further endorsed in focus groups we conducted in December 2021 and January 2022 with three occupational therapists and a developmental psychologist who prescribe JettProof sensory garments for their autistic clients. These focus groups further enabled us to explore additional considerations clinicians take into account when prescribing these garments for autistic children. One view expressed among participants in the focus group was that the choice and regimen of JettProof sensory garments should be individualized and informed by the child. Another view was that garments should be used adjunctive to other therapies rather than as standalone support. Lastly, of the range of garments manufactured by JettProof, the singlet was the most strongly endorsed and prescribed by clinicians for autistic children.

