#### 6.4. STUDY DESIGN

This single-subject case series will utilize an ABA design, where the intervention phase (b) is sandwiched between an initial baseline period (a) and post-intervention/return-to-baseline period (a). Each baseline period will last for one-week and involve unrestricted standard care. The intervention period will last for three-weeks, allowing a one-week acclimatization period before a two-week full-scale wearing protocol (if tolerable to the child). The full-scale wearing protocol was defined – through analysis of existing testimonial data, and consultation with JettProof and prescribing clinicians – as a minimum 6 hours/day of continuous wear. The participants will comprise children aged 4 years 0 months to 11 years 11 months with an existing community diagnosis of autism spectrum disorder (see Section 6.8. for a full description of trial inclusion/exclusion criteria). Child participants will attend six face-to-face assessment sessions with their caregiver(s): upon study entry (week 0), during pre-intervention/baseline phase A (week 1), pre-intervention/acclimatization phase B (week 2), intervention phase A (weeks 3 and 4), and post-intervention/return to baseline phase A (week 5).

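### The primary motor tests, and three caregiver questionnaires, are scheduled only in the two off-singlet weeks, so no on- versus off-singlet contrast can be computed for them

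*Protocol*

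**What the plan says.** The design in Section 6.4 is ABA: "the intervention phase (b) is sandwiched between an initial baseline period (a) and post-intervention/return-to-baseline period (a". Week 1 is the first A phase. Section 6.8.B makes week 2 acclimatisation and weeks 3 and 4 full intervention, and then says "Children will cease wearing their singlet and return to their standard care in week 5".

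Five instruments are placed only in weeks 1 and 5:

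- M-ABC-2 and COMPS-2, the primary motor outcome: Section 6.7.A ("in weeks 1 and 5. The M-ABC-2 is one of the most widely used motor assessments") and Section 6.8.C ("Additional assessments conducted at weeks 1 and 5 include the M-ABC-2 and COMPS-2").
- SCAS-P, child anxiety, secondary: Section 6.7.B ("in weeks 1 and 5. The SCAS-P has strong properties").
- PES, caregiver effort, listed among the other outcomes: Section 6.7.C ("in weeks 1 and 5. The PES has shown adequate internal consistency").
- PSI-4-SF, caregiver stress, also in Section 6.7.C ("in weeks 1 and 5. The PSI-4-SF has shown good internal consistency").

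Table 1 agrees for all five. Section 6.8.C, read alone, could suggest that SCAS-P and PES are given weekly alongside GAS, but Table 1 and Sections 6.7.B and 6.7.C settle the matter. No section says that the singlet is worn during the week 5 tests. The registry data set in Section 2.2.B gives the timing of these measures only as pre-post.

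**The concern.** The objectives in Section 6.3 concern what happens when the singlet is applied: better motor functioning, less anxiety, less caregiver stress and effort. Section 6.2 promises to compare each child's response to the intervention with that child's own baseline. For these five instruments nothing is recorded in the intervention phase.

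The schedule also conflicts with the design's own logic. In an ABA design the second A phase is where a reversible benefit should fade, yet here it is the only follow-up. Section 6.1 makes a reversible effect the natural expectation: "testimonials suggested a short duration of effect (i.e., only while wearing".

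Two misreadings follow. A null result could be reported as no effect on motor coordination when the singlet was not on at either test. A positive result could be credited to the singlet when it came from retesting, the passage of time or other care, which Section 6.6.F leaves unrestricted. Section 6.9 says that the study is meant to supply preliminary effect sizes, and for these outcomes they would describe the wrong contrast. Once the visits have passed, the missing observation cannot be recovered.

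**Working it through.** **Observations per child by phase.** Inputs are Table 1 and the phase labels in Sections 6.4 and 6.8.B (A1 = week 1, B = weeks 2 to 4, A2 = week 5).

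| Measure | A1 | B | A2 |
|---|---|---|---|
| M-ABC-2, COMPS-2, SCAS-P, PES, PSI-4-SF | 1 | 0 | 1 |
| E4 recordings, Lab-TAB, GAS | 1 | 3 | 1 |

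The GAS row follows Table 1 and Section 6.8.C; Section 6.7.A gives GAS ratings only in weeks 1 and 5. The weekly visits in phase B already exist, so the gap lies in what is done at them.

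**What the planned analysis can use.** Section 7.3.A plans slope and level change across phases, Hedges g and non-overlap indices, and lists both PES forms and the PSI-4-SF among the repeated measures. With no B point, no A-versus-B index exists for any of the five. For A1 against A2 within a child, the pooled SD has 1 + 1 − 2 = 0 degrees of freedom, and the smallest one-sided permutation p-value is 1/C(2,1) = 0.5.

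**What the two differences estimate.** Let δ be the effect while wearing, c the fraction of it that persists into week 5, and τ4 and τ5 the change by weeks 4 and 5 from practice, time and other care.

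- Week 5 − week 1 = cδ + τ5. With c = 0 this is τ5 alone, whatever δ is. With c > 0, cδ and τ5 cannot be separated.
- Week 4 − week 1 = δ + τ4, if the singlet is worn at the week 4 test.
- Week 4 − week 5 = (1 − c)δ − (τ5 − τ4). This is the reversal, and it helps to tell δ from a steady trend.

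**Illustration only.** The protocol names no group test and states no effect size. Assume a two-sided paired t-test at 0.05 with n = 10, an on-wear effect d in SDs of the differences, and no practice or time effect. Power comes from the non-central t with 9 df and non-centrality c·d·√10. For d = 0.8 it is 5%, 9%, 21% and 62% at c = 0, 0.25, 0.5 and 1. For d from 0.5 to 1.2 at c = 0.5 it is 11% to 40%. The 5% at c = 0 is the significance level by construction.

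**Visit time.** The synopsis states 9 hours. From Sections 6.8.A and 6.8.C, weeks 0 to 5 give 2 + 2 + 1 + 1 + 1 + 2 = 9, which reproduces it. A two-hour week 4 visit gives 2 + 2 + 1 + 1 + 2 + 2 = 10.

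**What one added point buys.** With two A points and one B point, the smallest one-sided p-value within a child is 1/C(3,1) = 0.33. The gain is a descriptive or pooled on-versus-off contrast, not significance for a single child.

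**The case against.** The best defence is that the protocol openly declares a pre-post comparison for these measures, and that three weeks of wear might leave a lasting change that week 5 would show. The evidence for a short effect is thin: it comes from customer testimonials, which also reported delayed onset, and motor coordination is not among the effects listed there. This stands in part. A reader might infer that the trial cannot detect any effect of the singlet on these outcomes; that holds only without carry-over. A persisting effect could appear in week 5, though it could not be told apart from practice, time or other care.

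The five instruments are also not equal. A motor test records performance on the day. A caregiver questionnaire may look back, and neither the recall windows nor the day of the week 5 visit is stated. The documents do not establish that the questionnaire answers would exclude week 4. This stands, and it makes the case weaker for SCAS-P, PES and PSI-4-SF.

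It might further be inferred that half of the primary objective goes unanswered. That is too strong. Motor coordination is one of three primary outcomes. The E4 recordings, which include motion-based activity, are scheduled in every week from 1 to 5, as are GAS ratings in Table 1. Those do not replace a motor test, but phase B is not unobserved.

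Finally, this is a feasibility study of ten children with no power claim. That tempers how much any result can show, but it does not justify leaving a primary outcome unmeasured in the intervention phase.

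**Conclusion.** The point holds. As scheduled, M-ABC-2, COMPS-2, SCAS-P, PES and PSI-4-SF have 1/0/1 observations by phase, and no on- versus off-singlet contrast can be formed. This count needs no assumption beyond the stated schedule.

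That the difference between weeks 5 and 1 says nothing about the wearing effect depends on that effect stopping with removal, which the protocol's background suggests but does not prove. If some effect persists, the difference is informative but confounded. The conclusion is firm for the motor tests and more tentative for the three questionnaires.

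The power figures illustrate how the loss depends on carry-over under assumed effects and a test that the plan does not name. They should not be quoted as properties of this trial.

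**What to change.** In Sections 6.7.A to 6.7.C, Section 6.8.C and Table 1:

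- Schedule M-ABC-2 and COMPS-2 at the existing week 4 visit, and preferably SCAS-P, PES and PSI-4-SF as well.
- Record whether the singlet is worn during the motor tests. Section 6.8.B leaves wearing times and contexts open, so a week 4 test is not on-singlet by default.
- Name week 1 versus week 4 as the main contrast and keep week 5 as the return-to-baseline check.
- Replace the pre-post timing in the Section 2.2.B registry data set with the matching weeks.

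The cost is a protocol and registry amendment, about one extra visit hour per child (9 to about 10) and one more retest, with its own practice effect.

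If burden must not rise, the battery could move from week 5 to week 4. That loses the reversal point, leaving one A and one B observation and no check on practice or time. Nor should it be assumed to hold the total at 9 hours: the child and caregiver interviews remain in week 5, so that visit may not shrink to one hour.

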#### 5.1.D. RESEARCH TEAM

See section 5.1 for members. The Principal Investigator is responsible for the design, conduct, and completion of this research project, for preparation of the project protocol and revisions, for corresponding with the HREC and ensuring appropriate approvals have been obtained, for ensuring compliance with the project protocol and applicable laws and regulations and institutional policy governing the research, for preparation of progress, safety, compliance, financial, and a final reports to the HREC and study funder, for preparation of research publications and for managing the conduct of the Lead Co-Investigators and Co-Investigators.

The Lead Co-Investigator will contribute to preparation of the project protocol (and revisions), documentation, reports and publications and be responsible for recruiting participants, liaising with the Principal Investigator and other individuals consulting on the trial, for executing the project in accordance with the protocol and applicable laws and regulations and institutional policy, for maintenance of data systems and data verification, and for coordination with Co-Investigators to conduct research assessments, and will provide agreement on the final protocol.

The Co-Investigators will be responsible for implementing appropriate safety procedure and practices for the research project, liaising with caregivers of child participants including to monitor for adverse events, for implementing the study protocol of procedures and assessments, and will provide agreement on the final protocol.

The Research Assistants will support the Lead Co-Investigator and Co-Investigators to implement study procedures, including the completion of research assessments and associated data preparation and management.

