## 6.3. OBJECTIVES

This study will test the use of JettProof sensory singlets among children with a diagnosis of Autism Spectrum Disorder. The primary objective of this trial is to evaluate the effects of JettProof sensory singlets – applied for at least 6 hours/day for a three-week period – on the self-regulatory and motor functioning of autistic children. We hypothesise that application of the JettProof sensory singlet will lead to a reduction in autonomic and behavioural markers of affective and motor dysregulation and the subsequent attainment of individualized goals, relative to standard care.

A second objective is to evaluate the effects of JettProof sensory singlets on additional outcomes related to sensory and motor functioning difficulties for autistic children and their caregivers. We hypothesize that, for children, the application of the JettProof sensory singlet will lead to a reduction in anxiety, less negative and more positive daily affect, and improvements in sleep quality for children and, for caregivers, a reduction in the levels of stress and perceived effort required to assist their children.

A third objective is to assess the feasibility and acceptability of implementing JettProof sensory singlets with autistic children. We anticipate that most children will wear the singlet for 6 hours/day or more during the full-scale intervention phase, and report that it is at least tolerable.

A fourth, exploratory objective is to determine whether there may be sensory characteristics of autistic children that predict differential response to JettProof sensory garments. We hypothesize that JettProof sensory singlets will evidence greater efficacy among children with a dysfunction in proprioceptive and/or vestibular sensory systems.

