**Child Assessment Measures**

Assessment Tool	Description		
Movement Assessment Battery for Children-2 nd Edition (M-ABC-2; Henderson et al., 2007)	Standardized direct assessment of child motor function	Component standard scores; Total standard score	Outcome
Clinical Observations of Motor and Postural Skills-2 nd Edition (COMPS-2; B Wilson et al., 2000)	Observational direct assessment of child motor and postural skills	Domain score; Total score	Outcome

**Study Name:** Effectiveness of JettProof Sensory Singlets for Autistic Children: A Single Case Series

**Protocol Number:** N/A

**Version & date:** version 2, dated 18th July 2022

Empatica E4	Wearable biosensor to collect peripheral physiological arousal and motion activity	Heart rate; Heart rate variability; Electrodermal activity; Motion-based activity	Outcome
Laboratory Temperament Assessment Battery (Lab-TAB; H. Goldsmith et al., 2010)	Standardized direct assessment of child self-regulation	Task scores; Composite score	Outcome
Interview	Examiner-led interview to ascertain children’s own motivations and experiences	Qualitative responses to interview questions	Feasibility/acceptability

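### Nothing in the protocol keeps the scorer of the Lab-TAB films (and of COMPS-2, where it is scored from film) from knowing the trial week, and in a fixed-order ABA series the week reveals the phase

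*Protocol*

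**What the plan says.** Section 6.8.C sets the visit procedures and states: "All assessment sessions will be video-recorded with consent from caregivers for later scoring". The filmed visits include Lab-TAB in weeks 1 to 5. The same section adds: "Additional assessments conducted at weeks 1 and 5 include the M-ABC-2 and COMPS-2".

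Section 6.7.B lists among the secondary outcomes "Child reactivity and self-regulation as coded from behaviour during semi-structured Lab-TAB" episodes, and gives the reason for including them: "Being a direct observational method, the Lab-Tab will provide a method by which to build upon and complement caregiver" reports of affect.

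Section 6.7.A makes motor performance a primary outcome: "Child motor coordination as measured by the standardized Movement Assessment Battery for Children-2", together with COMPS-2. Table 2 describes COMPS-2 as "Observational direct assessment of child motor and postural skills".

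Section 6.3 gives a directional hypothesis: the singlet "will lead to a reduction in autonomic and behavioural markers of affective and motor dysregulation".

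On staffing, Section 5.1.D says: "The Research Assistants will support the Lead Co-Investigator and Co-Investigators to implement study procedures, including the completion of research assessments", and adds the related data preparation. No scorer of the films is named in the text available.

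**The concern.** Lab-TAB coding and COMPS-2 scoring rest on a rater's judgement. The hypothesis has a stated direction, there is no control arm, and the phase order is the same for every child. A scorer who knows the week can therefore mark ambiguous behaviour in line with what the phase is expected to show.

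This matters because most of the other outcomes come from caregivers, who know when the singlet is worn and cannot be masked. The protocol offers Lab-TAB as direct observation to stand beside those caregiver reports. If its coder also knows the phase, part of that complementary value is lost. The protocol does not need new data collection to avoid this, because the films are already planned.

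Who scores, what they know and in what order they see the clips are matters of trial conduct. They have to be settled before coding starts, and a statistical analysis plan cannot restore masking once films have been scored with the week known.

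**Working it through.** No stated figure bears on this point, so the check compares sections.

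**1. Does week identify phase?** Sections 6.4 and 6.8.B give one order for all children: week 1 baseline, week 2 acclimatisation, weeks 3 and 4 full wear, week 5 return to standard care. The study is non-randomised (Section 2.2.B). Week and phase are therefore the same information.

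**2. Which outcomes depend on a rater who could be masked?** (Sections 6.7 and 6.8.C, Tables 1 and 2)

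| Outcome | Status | Weeks | Source | Can the rater be masked? |
|---|---|---|---|---|
| Empatica E4 signals | primary | 1 to 5 | device | no rater involved |
| GAS | primary | 1 to 5 in Table 1 | caregiver | no |
| M-ABC-2 | primary | 1 and 5 | examiner, possibly live | only if scored from film |
| COMPS-2 | primary | 1 and 5 | examiner observation | yes, where scored from film |
| Lab-TAB | secondary | 1 to 5 | coder | yes; incomplete in weeks 2 to 4 if the singlet shows |
| SCAS-P, daily affect and sleep, PES, PSI-4-SF | secondary or other | various | caregiver | no |

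**3. Is there any masking in the text?** None was found: no masked scorer, no separation of scoring from visit conduct, no shuffled or unlabelled clips, and no heading in the table of contents that would cover it. Two sets of statements might be mistaken for it. The independence statements in Sections 4 and 5.1.B concern the funder and the manufacturer, not knowledge of phase. The reliability remarks in Section 6.7.A concern the published instruments, not scoring in this trial.

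**4. Could the scorer know the phase?** Research assistants help complete assessments and prepare data (Section 5.1.D), and the occupational therapist research assistant goes over the visual schedule, which shows singlet wearing, at each visit (Section 7.5). The protocol does not say that these people score the films, and it does not say that they do not. The films may also reveal the phase: the week 5 visit includes an interview about the singlet (Section 6.8.C), the schedule review may be recorded, and the singlet may be visible in weeks 2 to 4.

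**5. What would a scorer shift do?** Write the observed phase contrast as δ + b, with δ the true change and b the shift from knowing the phase. Recruiting more children narrows the uncertainty around δ + b but leaves b as it is. Lab-TAB is on the Section 7.3.A list of repeated measures to be plotted by phase; that section then calls for Hedges g, non-overlap indices such as Tau-U, and a .05 threshold. The shift would pass into those summaries.

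**6. Illustration only, on assumed values.** Take δ = 0, 10 children and a two-sided paired t-test at 0.05 (critical t = 2.262 on 9 df), with b in SDs of the within-child difference and noncentrality b × √10.
- b = 0: chance of p < .05 is 5.0%
- b = 0.2: noncentrality 0.63, chance 8.8%
- b = 0.5: noncentrality 1.58, chance 29.3%

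The protocol names no such group test and gives neither an SD nor a bias size. This shows how a shift could pass as an effect; it does not estimate the shift in this trial.

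**The case against.** The strongest reply has five parts.

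- **Silence is not permission.** A reader might infer that the staff who run the visits will score the films. The documents do not say so. Section 5.1.D gives research assistants assessments and data preparation, not film coding, and the member listing in Section 5.1 is not in the text available. This stands. The point is only that nothing withholds the week from whoever scores.
- **Other outcomes are free of rater judgement.** A reader might infer that the scored outcomes are the only ones that could escape expectation bias. They are not: the Empatica E4 signals are primary and device-recorded. This stands.
- **The motor tests are a weaker case.** M-ABC-2 is a standardised direct test and may be scored live. Both motor tests fall at weeks 1 and 5, off the singlet. Section 6.1 reports testimonials of benefit only while the garment is worn, so a scorer holding that view might expect week 5 to look like week 1. A bias in the hypothesised direction is therefore not established for motor skills. The motor measures are also absent from the list of repeated measures in Section 7.3.A. This stands.
- **No size can be given.** A reader might express an assumed shift as a share of a confidence interval for 10 children. Section 7.3.A describes within-child graphs and names no group paired estimate, and a shift in rating SDs equals a shift in Hedges g only if both use the same SD. This stands.
- **This is a small feasibility series**, and Lab-TAB is secondary. That limits the weight of the point but does not remove it, because Section 6.9 wants preliminary effect sizes from these data and the remedy uses films already planned.

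**Conclusion.** The concern holds in a limited form. The protocol plans later scoring from film and rater coding of Lab-TAB in weeks 1 to 5, in a design where week gives away phase, and it has no step that hides the week from the scorer. Lab-TAB is the clearest case; COMPS-2 follows to the extent that it is scored from film. For the motor tests the exposure is confined to the week 1 to week 5 comparison, with no settled direction.

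This is a risk that the plan leaves open, not a demonstrated bias, and its size cannot be derived from the documents. The conclusion assumes that masking is not described in the contributorship listing, which was not available. It is worth correcting before coding begins, because the change is cheap and cannot be made afterwards.

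**What to change.** Add to Section 6.8.C:

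- Films are cut to the task segments, leaving out interviews and the review of the visual schedule. Renaming files alone would not hide the phase.
- Clips carry random codes and are scored in random order after the child's last visit.
- The scorer is an existing team member who is not told the week and, where staffing allows, did not conduct that child's visits.
- For each clip, the scorer records whether the singlet could be seen and whether they guessed the phase.
- Motor items scored live, for example on M-ABC-2, are reported as unmasked.

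A rule that children wear an outer top at every visit is not proposed: it would add a clothing burden for children selected for sensory difficulties.

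Cost: protocol wording, some clip preparation, and coding that waits until each child has finished. Masking will remain incomplete in weeks 2 to 4 wherever the singlet is visible, and the scorer's record lets that be reported. Whether a scorer with no part in a child's visits can always be found depends on team size, which the available text does not show.
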